Evaluation of a “Fast Track” Respiratory Therapy Clinic for Patients with Suspected Severe Sleep-Disordered Breathing

STATISTICAL ANALYSIS PLAN

NCT#: 02191085

Document Date: February 16, 2017

Evaluation of a "Fast Track" Respiratory Therapy Clinic for Patients With Suspected Severe Sleep-Disordered Breathing

Statistical Analysis

This study will use a modified intention to treat analysis, in which results will be analyzed for patients who are randomized and have treatment adherence data three months after initiating PAP therapy.

Paired t tests will be used to compare clinical outcomes from baseline to 3 months and one year and unpaired t tests will be used to compare time to treatment initiation and measures of patient demand. Multiple logistic regression will be used to identify predictors of study outcomes using variables identified as predictive on univariate regression. Outcomes will be transformed into binary variables based on clinically relevant cut-offs.

The economic analysis will be performed using the perspective of a publicly funded healthcare system. An estimate of mean utility scores based on the HUI questionnaire will be calculated and the average quality-adjusted life- year (QALY) will be calculated for each study arm. Using bootstrapping, we will compare the difference in mean costs and QALYs between the study arms to generate an incremental cost-effectiveness ratio for an ACP-led clinic compared to traditional physician-led care. Sensitivity analyses will be performed to evaluate the effect of changes in physician fees, RT salaries, diagnostic testing costs and treatment costs.

All study outcomes will be analyzed in different subgroups to clarify the impact of ACP-led care for patients with different patient flow pathways or clinical treatments. Pre-specified subgroups include:

- Patients who undergo PSG vs. patients who do not undergo PSG
- Patients treated with bilevel PAP vs. patients treated with CPAP
- Patients who are treated with oxygen vs. patients treated without oxygen

Sample Size

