The study is powered to assess the non-inferiority of ACP-led care compared to usual care by sleep physicians. A non-inferiority margin of -1 hour of PAP adherence was determined by consensus of the investigators and has been used in previous studies comparing different models of care for SDB. One hundred thirty eight patients (69 in each arm) will be required to achieve 90% power with a type I error of 0.05, using this non-inferiority margin and a standard deviation of 2 hours of nightly CPAP use. The standard deviation used in the sample size calculation was based upon the results of two previous studies. To account for withdrawals and loss to follow-up (approximately 15% at the FMC Sleep Centre), recruitment will continue until three-month adherence data is available for 150 patients.

Reference: Ip-Buting A, Kelly J, Santana MJ, Penz ED, Flemons WW, Tsai WH, et al.

Evaluation of an alternative care provider clinic for severe sleep-disordered breathing: a study protocol for a randomised controlled trial. *BMJ Open*. 2017 Mar;7(3):e014012.

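### The SAP's only named cost-effectiveness summary is an ICER, with no provision for a QALY difference that is near zero or changes sign

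*SAP*

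**What the plan says.** The economic paragraph of the SAP (Statistical Analysis) takes the perspective of a public payer. On utilities it says: "An estimate of mean utility scores based on the HUI questionnaire will be calculated". It then derives an average QALY per arm and continues: "Using bootstrapping, we will compare the difference in mean costs and QALYs between the study arms", the stated purpose being "to generate an incremental cost-effectiveness ratio for an ACP-led clinic compared to traditional physician-led care".

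The sensitivity analyses concern cost inputs only: "Sensitivity analyses will be performed to evaluate the effect of changes in physician fees, RT salaries, diagnostic testing costs and treatment costs".

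Neither document mentions net benefit, a willingness-to-pay value, a cost-effectiveness plane, an acceptability curve, an interval for the ICER, or what to do if the QALY difference is negative or near zero. Neither gives an expected QALY difference or a QALY SD. The Protocol's Data Collection tables list the HUI and the cost sources but no economic method.

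The design premise is in the SAP's Sample Size section: "The study is powered to assess the non-inferiority of ACP-led care compared to usual care by sleep physicians". The margin is in hours of PAP use: "A non-inferiority margin of -1 hour of PAP adherence was determined by consensus of the investigators".

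**The concern.** An ICER is the cost difference divided by the QALY difference. Two problems arise when the denominator may be near zero.

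- **Instability.** Small changes in the QALY difference move the ratio by large amounts and can flip its sign. Bootstrap ratios then come from different quadrants of the cost-effectiveness plane, and their percentiles have no useful ordering.
- **Ambiguous sign.** Take a cost difference of −300 with a QALY difference of +0.02: the ratio is −300/0.02 = −15,000, and the ACP clinic is dominant. With +300 and −0.02 the ratio is again −15,000, and the clinic is dominated. (The figures are assumed, for illustration.)

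A finding that ACP-led care costs less at about equal QALYs would be useful to a public payer, and a ratio expresses it badly. The planned sensitivity analyses do not help, because they change the numerator only.

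**Working it through.** **1. The plan's own figure.** The SAP states "One hundred thirty eight patients (69 in each arm) will be required to achieve 90% power with a type I error of 0.05", with "a standard deviation of 2 hours of nightly CPAP use" and a margin of 1 hour. Per arm, n = 2(z_α + z_β)²SD²/margin². With one-sided α = 0.05 and a true difference of 0, this is 2 × (1.645 + 1.282)² × 4/1 = 68.5, rounded up to 69, or 138 in total. It reproduces. (One-sided 0.025 gives 85 per arm, 170 in total, which does not match.) The stated N therefore assumes no difference in adherence. It says nothing directly about QALYs.

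**2. Inputs for the ratio.** From the SAP: recruitment continues until 150 patients have three-month adherence data, so about 75 per arm with equal arms. Assumed, because the documents give none: QALY SD 0.10 to 0.30 and true QALY difference d of 0, 0.02 or 0.05.

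**3. Formulas.** SE of the QALY difference = SD × √(2/75). The 95% Fieller interval for a ratio is bounded only when the denominator differs from zero at the 5% level. Hence P(bounded) = Φ(d/SE − 1.96) + Φ(−d/SE − 1.96), which needs no cost assumptions.

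| QALY SD | SE | d = 0 | d = 0.02 | d = 0.05 |
|---|---|---|---|---|
| 0.10 | 0.0163 | 0.05 | 0.232 | 0.865 |
| 0.15 | 0.0245 | 0.05 | 0.129 | 0.532 |
| 0.20 | 0.0327 | 0.05 | 0.094 | 0.334 |
| 0.30 | 0.0490 | 0.05 | 0.069 | 0.175 |

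At d = 0 the estimated QALY difference is equally likely to be positive or negative. At d = 0.02 it is zero or negative with probability Φ(−d/SE) = 0.11, 0.27 and 0.34 for SD 0.10, 0.20 and 0.30. For a 90% chance of a bounded interval, d must be about SE × (1.96 + 1.2816) = 0.053, 0.106 and 0.159 respectively.

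**4. Fewer patients at one year.** If the SAP's 15% loss also applied between three months and one year (an assumption), n would be 150 × 0.85/2 ≈ 64 per arm. P(bounded) is then 0.05 at d = 0, 0.066 to 0.205 at 0.02, and 0.156 to 0.807 at 0.05 for SD 0.30 to 0.10.

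**5. Bootstrap illustration.** 300 simulated trials per scenario, 2,000 resamples each, 75 per arm. All cost inputs are assumed: skewed costs with SD 3,000, a true cost difference of −500 and a willingness to pay of 50,000 per QALY. Net monetary benefit (NMB) = 50,000 × ΔQALY − Δcost.

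| QALY SD | d | Trials with more than 2.5% of resamples on each side of zero QALYs | Median width, ICER percentile interval | Median width, NMB interval |
|---|---|---|---|---|
| 0.10 | 0 | 95.3% | 842,832 | 3,671 |
| 0.20 | 0 | 95.7% | 406,672 | 6,618 |
| 0.30 | 0 | 95.3% | 268,771 | 9,709 |
| 0.10 | 0.05 | 14.7% | 57,574 | 3,689 |
| 0.20 | 0.05 | 66.3% | 199,536 | 6,623 |
| 0.30 | 0.05 | 86.3% | 218,489 | 9,684 |

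The two widths are in different units (per QALY, and money) and should not be compared with each other. What matters is that the NMB width hardly changes with d, whereas the ICER percentile interval mixes quadrants whenever resamples fall on both sides of zero.

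**The case against.** There is a serious case on the other side, and most of it stands.

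- A reader might infer that the cost and QALY differences will not be examined separately. The SAP does not support that: the same sentence plans to compare both. What is missing is a reporting format and an interval for them.
- A reader might infer that the QALY difference is expected to be near zero. No document says so. The non-inferiority premise concerns hours of PAP use, and the SAP also compares time to treatment initiation, so a QALY gain from earlier treatment is possible. On the other hand, the Protocol first collects the HUI at the baseline visit and times follow-up from the treatment date, so part of such a gain could fall outside the measured period. That too is inference, since no QALY time horizon is given.
- A reader might infer that the SAP plans an invalid interval for the ICER. It names no ICER interval at all.
- A reader might infer that the ICER is bound to be uninterpretable. It is not: at SD 0.10 and a true difference of 0.05, the interval is bounded in 86.5% of trials.
- Net benefit does not cure imprecision. In the illustration with d = 0, true NMB is 50,000 × 0 + 500 = 500. The 95% half-width is about 3,671/2 ≈ 1,836 at SD 0.10 and larger at higher SDs, so the interval would usually include zero.

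What remains is that the ratio is the only named summary that combines cost and effect, and nothing is specified for the case in which it breaks down.

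**Conclusion.** The concern holds as a conditional point. If arm QALYs are similar, the bootstrapped ICER is likely to be unstable and its sign ambiguous, and the SAP pre-specifies no alternative. The size depends on the assumed QALY SD and true difference: instability is near certain at a difference of 0, likely at 0.02 across the whole SD range, and anywhere from unlikely to likely at 0.05. A true difference of about 0.05 (SD 0.10) to 0.16 (SD 0.30) would largely remove the problem.

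Severity is minor. The economic analysis is not the question the trial is powered for, the adherence comparison is unaffected, and the planned cost and QALY differences already carry part of the information. Pre-specifying the summary would also prevent its being chosen after the quadrant is known.

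**What to change.** Add to the economic paragraph of the SAP, before the data are analysed, that the same bootstrap resamples will be used to report:

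- incremental cost and incremental QALYs, each with a 95% bootstrap CI;
- incremental net monetary benefit with a 95% CI at willingness-to-pay values that the investigators state in advance;
- the cost-effectiveness plane and an acceptability curve.

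Keep the ICER as a point estimate with its quadrant stated. Do not make its reporting depend on whether the QALY interval excludes zero, since that would tie the presentation to a significance test.

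The cost is a sentence or two of SAP text. No extra data, patients or resampling are needed. The gain is a summary with a defined interval and a clear direction whatever the sign of the QALY difference. In the earlier −15,000 example, with an assumed 50,000 per QALY, net benefit is 50,000 × 0.02 + 300 = +1,300 in the dominant case and −1,300 in the dominated one. Imprecision from QALY variance at this sample size remains.
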